10.5.2. Subject Disposition

A detailed description of subject accountability including count of subjects included, exposed, completed (i.e., subjects who complete the study treatment) and discontinued along with the main reason for discontinuation will be generated for each treatment group and for all subjects. All withdrawals from the study, taking place on or after study drug injection, will be fully documented in the body of the Clinical Study Report.

Note that the actual study duration is for a period of maximum 4.5 months, with efficacy analyses being conducted at Day 28, 56, and 84 visits.

10.5.3. Demographic and Baseline Characteristics

Baseline will be defined as the last available and evaluable parameter value before and closest to the injection. If a rechecked value is used for baseline, it should be collected under the same conditions as for the planned baseline.

Baseline safety data will be presented along with subsequent safety values assessed during or after dosing.

10.5.4. Primary Safety Endpoint

The incidence of SAEs considered related to treatment will be presented overall and by study cohort.

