4. STUDY ENDPOINTS

4.1. PRIMARY ENDPOINTS

The main objective is to evaluate safety following injection of RZL-012 vs. placebo injection into submental fat. Skin irritancy and AEs related to injection procedure will be mainly evaluated for its frequency, severity and duration. Specifically, the assessment of the following AEs will be monitored: bruising, pain, induration erythema and swelling/edema.

In cohort 1a total of 12 subjects will be randomized to receive active treatment or placebo (2:1) and in cohort 2 16 subjects will be randomized (at least 4 placebo subjects will be randomized) in the 2 clinical sites. Each clinical site will have at least one active and one placebo at each study cohort.

Twelve (12) subjects from Cohort 1 (8 active and 4 placebo) will be injected with a maximal dose of 120mg/subject or with up to 2.4 mL of vehicle. If no serious safety concerns will be noted within 28 days of follow-up post-dose of subjects from Cohort 1 (e.g., prolonged severe pain or severe swelling following injection), the study will proceed to the additional 16 subjects of Cohort 2 that are designated to be injected with a maximal dose of 240 mg/subject for active treatment or up to 4.8 mL vehicle in 4 for at least 4 placebo subjects that will b randomized.

In case of serious safety concerns among subjects receiving the 120 mg dose, sponsor and DSMB review may decide to reduce or remain with the 120 mg/subject dose level for remaining subjects.

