6.1.15.1. Evaluation of Primary Endpoints

6.1.15.1.1. Safety and Tolerability Monitoring

For determination of the study's primary end point, evaluation of safety and tolerability will be conducted according to definitions and guidelines below.

Safety and tolerability will be assessed by the study medical staff (e.g., PI, site coordinator, and study nurse) and the study subjects on the basis of the following:

- 1. AEs related to skin condition and injection procedure, general AEs and SAEs, including severity, relation to study treatment and classification by whether or not these events comprise intolerable side effects.
- 2. Physical exams, Draize score and vital signs measurements.
- 3. Subjects questioning full medical history during screening, routine AE reporting.

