7.2. SAFETY MEASUREMENTS

Safety measurements will be performed by monitoring the specific skin AEs: bruising, pain, induration, erythema and swelling/edema that have been identified as being associated with the use of RZL-012 investigational product. The AEs of RZL-012 vs. placebo will be evaluated for their frequency, severity and duration.

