10. STATISTICAL CONSIDERATIONS

10.1. STUDY DESIGN AND OBJECTIVE

This study is planned as a single blind, randomized, placebo-controlled, Phase 2a, 2-cohort study for the treatment of submental fat. Eligible subjects will be randomized to receive either RZL-012 or placebo (vehicle) in each study cohort and will be monitored for safety and efficacy during 84 days of follow up.

Primary objective:

The main objective is to evaluate safety following injection of RZL-012 vs. placebo into submental fat. Skin irritancy and AEs related to the injection procedure will be evaluated for frequency, severity and duration. Specifically, tolerability and assessment of the following AEs will be monitored: bruising, pain, induration erythema and swelling/edema.

Secondary Endpoints:

Secondary endpoints will test the efficacy of RZL-012 vs. placebo according to the following measures:

- 1. Improvement of Physician's global assessment questionnaire for treatment efficacy in active vs. placebo treated subjects at Day 28, 56 and 84 following injection.
- 2. Reduction from baseline in submental fat volume as measured by MRI, in RZL-012 treated subjects vs. placebo treated subjects at Day 84 following injection.
- 3. Improvement from baseline in the self-assessment of submental fat using the Face-Q satisfaction questionnaire rating score in RZL-012 treated subjects vs. placebo treated subjects on Days 28, 56 and 84.

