10.2. STUDY ENDPOINTS

10.2.1. Primary Safety Endpoints

Skin AEs will be evaluated for their frequency, severity and duration. Specifically, the assessment of the following AEs will be monitored among RZL-012 vs. placebo treated subjects: bruising, pain, induration, erythema, and swelling/edema.

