10.5. STATISTICAL ANALYSIS

10.5.1. General

Statistical analyses will be mainly descriptive in nature where study data will be tabulated and summarized using the mean, standard deviation or standard error. The results will be presented overall per cohort and per treatment.

AEs related to injection and Draize scores will be presented in tabular format by visit, cohort and treatment.

Improvement in Global physician's scale score pf RZL-012 treated subjects vs. placebo treated subjects by cohort and overall.

The average change from baseline in submental volume as analyzed from MRI images will be presented in a tabular form by treatment received (RZL-012 / placebo) by cohort and overall.

The average change in Face Q questionnaires score from baseline will be presented in a tabular form by treatment received (RZL-012 / placebo) by cohort and overall.

Any statistical tests will be two-sided. The required significance level (p value) of findings will be equal to or lower than 5%.

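### The section headed Primary Safety Endpoint (10.5.4) analyses only related SAEs, while the primary endpoint is the frequency, severity and duration of five local reactions; their duration is analysed nowhere in 10.5

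*Combined protocol and SAP*

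**What the plan says.** **The endpoint.** Section 10.2.1 sets the primary safety endpoint: "Skin AEs will be evaluated for their frequency, severity and duration". It then names bruising, pain, induration, erythema and swelling/edema, compared between RZL-012 and placebo. Section 4.1 says the same ("Skin irritancy and AEs related to injection procedure will be mainly evaluated for its frequency, severity and duration"), as does 10.1 ("Skin irritancy and AEs related to the injection procedure will be evaluated for frequency, severity and duration"). Section 7.2 makes the comparison explicit: "The AEs of RZL-012 vs. placebo will be evaluated for their frequency, severity and duration". Section 6.1.15.1.1 is broader and includes SAEs: "AEs related to skin condition and injection procedure, general AEs and SAEs, including severity, relation to study treatment".

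**The analysis under that name.** Section 10.5.4 consists of one sentence: "The incidence of SAEs considered related to treatment will be presented overall and by study cohort".

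**Elsewhere in 10.5.** Section 10.5.1 gives a general rule, "The results will be presented overall per cohort and per treatment", and one specific to local effects, "AEs related to injection and Draize scores will be presented in tabular format by visit, cohort and treatment". Section 10.5.6 tabulates all AEs by body system, preferred term, seriousness, severity and relation, by cohort. Section 10.2.3 lists AE and SAE incidence by severity, RZL-012 versus placebo, as a safety endpoint.

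**What is collected.** Section 6.1.14 assigns Draize to erythema and edema, the NRS to pain, and Table 3 to bruising and induration. For each AE it requires a start date, an end date or ongoing status, and a severity.

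**The concern.** The analysis written under the primary endpoint's own heading is not an analysis of that endpoint. An SAE under 9.1.2 needs an outcome such as death, hospitalization, disability or an important medical event. The reactions of interest will mostly fall short of that. Section 3.2 reports no SAEs linked to the earlier dose per site, spacing or maximal total dose. Section 1.2.4.1.2 reports that injection-site pain and edema were the most common AEs with an apparent causal link. The 10.5.4 table could therefore be empty while local reactions are common, severe or prolonged.

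If the plan is followed exactly, the duration part of the primary question goes unanswered. The frequency and severity parts are answered visit by visit, but not for certain subject by subject.

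**Working it through.** The documents give no power, event rate or duration figure for this endpoint, so there is no number to reproduce. The check sets the endpoint against each part of 10.5 and then sizes what is left open.

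**1. Coverage**

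| Dimension | 10.5.4 | 10.5.1 | 10.5.6 with 10.2.3 | Left open |
|---|---|---|---|---|
| Frequency | related SAEs only | by visit, cohort, treatment | by preferred term; subjects or events not stated | subjects ever affected |
| Severity | none | Draize by visit | general AE severity | worst grade per subject on the assigned scale |
| Duration | none | none | none | all of it |

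Within 10.5 the word duration occurs only in 10.5.2, for the length of the study.

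**2. Frequency.** Let c be the affected count at each visit among n subjects. The number ever affected lies between max(c) and min(n, sum of c). As an illustration, not a forecast, take n = 8 (active, cohort 1) with 4, 3 and 2 affected on Days 7, 14 and 28:

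- lower bound: max(4, 3, 2) = 4, or 50%;
- upper bound: min(8, 4 + 3 + 2) = 8, or 100%.

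If 10.5.6 counts subjects, it settles this number for reactions entered as AEs. If it counts events, it does not. The text does not say which.

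**3. Severity.** The same applies to worst grade. Suppose one subject has grade 3 on Day 1 and one subject has grade 3 on Day 7. The by-visit tables cannot show whether that is 1 of 8 (12.5%) or 2 of 8 (25%) with worst grade 3.

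**4. Duration.** Where a reaction is entered as a dated AE, duration is end date minus start date. Two gaps remain.

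- Unresolved reactions: one recorded as ongoing has no end date, and 10.6 imputes nothing. Without a censoring rule, the longest reactions drop out of any mean. This is not hypothetical: in the earlier Phase 2a study, one subject still had erythema and edema up to Day 140, which is 140 − 84 = 56 days past this study's last visit.
- Scores without a dated AE: visits fall on Days 1, 7, 14, 28, 56 and 84. A reaction seen only at Day 28 lasted more than 0 and less than 56 − 14 = 42 days. With the ±1 day window in 6.2.6 the upper limit is 57 − 13 = 44 days.

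**5. Which follow-up to use.** Every subject is scheduled to Day 84 (6.1.14, Appendix I). Section 9.5.1 follows ADRs to resolution or 6 months, about 182.6 − 84 = 98.6 days further with no scheduled visit. That extension applies only to events judged related (9.1.3). The investigator makes that judgement (9.3) and knows the treatment (3.1, 6.2.2). Day 84 is the horizon that both arms share regardless of causality.

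**6. Precision.** One subject is 1/8 = 12.5 percentage points on active and 1/4 = 25 on placebo in cohort 1. In cohort 2, active has at most 16 − 4 = 12 subjects, so one subject is at least 8.3 points.

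**The case against.** The strongest reply is that the plan is descriptive and 10.5 should be read as a whole. Section 10.5.1 gives local reactions by visit and by arm. Sections 10.5.6 and 10.2.3 promise AE incidence by preferred term and severity, which many programmers would produce as subject counts at maximum severity. SAEs belong to the primary evaluation under 6.1.15.1.1, so 10.5.4 is incomplete rather than irrelevant. Much of this stands: frequency and severity are partly covered. It does not reach duration, and it leaves the counting unit and worst-grade rule to convention.

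Several stronger readings are tempting, but the documents do not support them:

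- **No arm comparison is planned.** Sections 10.5.4 and 10.5.6 say only by cohort, but the general rule in 10.5.1 adds treatment. This is loose wording.
- **No scale is assigned.** Sections 6.1.7 and 6.1.14 assign one to each reaction.
- **Nothing separates pre-injection findings.** Section 9.1.1 limits AEs to findings that are new or worse than baseline, and 10.5.3 defines baseline. The fix only carries this through.
- **Three follow-up periods conflict.** Screening, follow-up and the MRI window give 45 + 84 + 5 = 134 days, about 4.4 months, within the 4.5 months of 10.5.2. The 6 months in 9.5.1 is follow-up of ADRs already identified.
- **Unblinded physicians would define the missing summaries after seeing the data.** They are unblinded, but nothing says they define the analyses.
- **The earlier Day 140 case was drug-related.** The protocol does not say how that case was judged.

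**Conclusion.** The point holds as a mismatch between endpoint and analysis. Section 10.5.4 does not analyse the primary endpoint defined in 4.1, 7.2, 10.1 and 10.2.1. Of the three stated dimensions, duration has no analysis in 10.5. Frequency and severity have by-visit and general AE tables, but no stated subject-level summary.

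It should be fixed before the data are analysed. It does not threaten the design: no sample size, significance level or power figure depends on it, and the data needed are largely collected already. The conclusion rests on the text alone. The 4/8 to 8/8 range is an illustration with assumed counts, and it narrows to a single number if 10.5.6 is confirmed to count subjects and every reaction is entered as an AE.

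**What to change.** Rewrite 10.5.4 so that, for each of the five reactions, in the SA set, by treatment within cohort and irrespective of causality, it reports:

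- (a) number and percentage of subjects with any post-injection onset, or worsening from the pre-injection grade;
- (b) worst post-injection grade per subject, on the scale assigned in 6.1.7 and 6.1.14 (Draize, NRS or Table 3);
- (c) duration from AE start and end dates through Day 84, with reactions unresolved at Day 84 or at earlier withdrawal treated as censored, and the number unresolved at Day 84 stated.

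List ADR follow-up after Day 84 (9.5.1) separately as supportive, because entry to it depends on an unblinded relatedness judgement. Keep related SAEs as a supporting table by cohort and treatment, and use the same split in 10.5.6. Keep the by-visit tables of 10.5.1.

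The cost is SAP wording and a few descriptive tables, which will be imprecise with arms as small as 4 and 8. Dates, severity and outcome are already required for each AE. The documents do not say that every non-zero Draize, NRS or Table 3 score becomes a dated AE, so a short CRF rule to that effect is needed.

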10.5.5. Efficacy Analysis

The change from baseline of submental fat volume will be presented in tabular form by treatment and dose.

The changes from baseline in FACE-Q score as a function of treatment group will be presented in tabular form per treatment group and dosing group.

10.5.6. Safety and Tolerability

Safety analyses will be descriptive in nature.

All reported AEs will be coded to a standard set of terms using MedDRA coding dictionary (V.22 or higher) treatment.

AEs and tolerability data will be presented descriptively by study cohort. AEs will be tabulated by body system, preferred term, seriousness, severity and relation to study drug by cohort.

10.6. HANDLING OF MISSING DATA

No imputation of missing data will be performed.

10.7. INTERIM ANALYSIS

No interim analysis is planned.

11. DATA COLLECTION, STUDY MONITORING, AND DATA DISCLOSURE

11.1. DATA COLLECTION AND REPORTING

Each study subject will be assigned an individual CRF that will contain all of the relevant study information. The investigator shall ensure that all data is completely and accurately recorded on the CRFs throughout trial duration.

Data reported on the CRF that are derived from source documents should be consistent with the source documents or the discrepancies should be explained.

All fields and blanks in the CRFs will be completed. The following abbreviations are to be used when values or answers are not available: NA = Not applicable, ND = Not done, UNK = Unknown, CONT = Continued.

Any change or correction to a CRF should be dated, initialed, and explained (if necessary) and should not obscure the original entry (i.e., an audit trail should be maintained). If an entry on a CRF form is changed, the correction will be made as follows: A single line will be drawn through the incorrect entry, the date and initials of the reporting individual will be added beside the entered change and/or correction, and an explanation will be added when applicable.

When a subject withdraws from the study, regardless of cause, all final study evaluations should be attempted.

If a subject is lost to follow-up, (i.e., fails to return for scheduled visits) every reasonable effort must be made to contact the subject in order to determine why the subject failed to return. All actions taken in this regard will be documented and dated in the CRF.

Once completed, a copy of each completed CRF will be signed and dated by the investigator or a designated representative and submitted to the Sponsor.

11.2. RECORD KEEPING

The investigator will maintain all records for this study including medical records, laboratory reports, ICFs, safety reports, subjects' CRF, and any other pertinent data. All records are to be retained by the investigator for a period of seven years after completion of the study.

11.3. SOURCE DATA AND SOURCE DOCUMENTS

ICH-GCP defines source data as all information in original records and certified copies of original records of clinical findings, observations, or other activities in a clinical trial necessary for the reconstruction and evaluation of the trial. Source data are contained in source documents (original records or certified copies).

Source documents are defined as original documents, data, and records (e.g., hospital records, clinical and office charts, laboratory notes, subject files, and records kept at departments involved in the clinical trial, etc.).

The following data is to be recorded directly on the RZL-012 trial forms or CRF, which will be considered to be the source data:

- Subjects' questioning, e.g., pain, itching, topical antihistamine application.
- Assessment of AEs relation to investigational product, i.e., causality assessment, and expectedness reported by investigator.

The investigator should maintain the trial's essential documents as required by ICH-GCP guidelines and the applicable regulatory requirements, and take measures to prevent accidental or premature destruction of these documents.

Upon request of the monitor, auditor, IRB/EC, or regulatory authority, the investigator will ensure direct access to all requested trial-related records.

11.4. STUDY MONITORING

Monitoring procedures are required to assure compliance to ICH-GCP guidelines, the study protocol and local regulations.

The investigator shall allow the Sponsor or its official designee to monitor and audit periodically, at mutually convenient times, all CRF and corresponding subject records. The monitoring schedule will be based on Sponsor's monitoring plan and will be done by competent monitors per GCP by either Sponsor personnel or sponsor's designee such as a Clinical Research Organization (CRO).

11.5. CONFIDENTIALITY, DATA DISCLOSURE, AND PUBLICATION

In order to protect subject confidentiality, a consecutive identification number will be attributed to each subject enrolled to the trial, at each site. In order to avoid identification errors, this number and subject's initials (first letter of first name and the first letters of surname) will identify the subject and must be included on all CRFs. The investigator will complete subject identification on a confidential site log, which will be used for subjects' traceability and follow-up.

Individual subject medical information obtained as a result of this study is to be considered confidential and disclosure to third parties other than the regulatory authorities, or other persons or organizations designated by the Sponsor, is prohibited. Any medical information may be provided to the subject's personal physician or to appropriate medical personnel responsible for the subject's care. Additionally, data generated from this study is to be provided, upon request, to the Sponsor's monitors, as well as to the local IRB/EC. Subject confidentiality is to be further assured by utilizing subject identification code numbers to identify subject data.

All information supplied by Raziel Therapeutics Ltd. in connection with this study and not previously published, is considered confidential information. This information includes, but is not limited to, the IB, clinical protocol, CRF, and other scientific data. Any data collected during the study are also considered confidential. This confidential information shall remain the sole property of Raziel Therapeutics Ltd, shall not be disclosed to others without the written consent of the Sponsor, and shall not be used except in the performance of this study. The information developed during the conduct of this clinical study is also considered confidential, and will be used by the Sponsor in connection with the development of the product. The information may be disclosed as deemed necessary by the Sponsor. To allow the use of the information derived from this clinical study, the investigator is obliged to provide Raziel Therapeutics Ltd. with complete test results and all data developed in this study.

The Sponsor has full ownership of the original CRFs completed as part of the study.

By signing the clinical study protocol, the investigator agrees that the results of the study may be used for the purposes of national and international registration, publication, and information for medical and pharmaceutical professionals. The authorities will be notified of the investigator's name, address, qualifications, and extent of involvement.

The information obtained during this study may be made available to other investigators who are conducting similar studies.

It is agreed that, consistent with scientific standards, publication of the results of the study shall be made only as part of a publication of the results obtained by all sites performing the protocol.

Raziel Therapeutics Ltd. will disclose the results of the trial on the basis of the final analysis and following the revision of a draft manuscript by the investigators, unless posting would compromise publication in a peer-reviewed medical journal or contravene national laws or regulations. Study results may also be disclosed through presentations and abstract submissions at professional scientific meetings.

12. HUMAN SUBJECTS

12.1. DECLARATION OF HELSINKI

Both the PI and the Sponsor will ensure that the study is conducted in agreement with the Declaration of Helsinki, ICH-GCP, and the local laws and regulation.

